2.2 SECONDARY OBJECTIVES

2.2.1 To determine the rate of severe acute toxicity, defined as any CTCAE v4 grade 3 or higher toxicity noted from RT delivery up to 90 days after completion of surgery.

2.2.2 To determine the rate of poor cosmetic outcomes from both provider and patient perspectives up to 3 years after pre-operative SBRT to intact breast tumors using the RTOG (Radiation therapy oncology group) cosmesis scale and digital images.

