9. CRITERIA FOR EVALUATION AND ENDPOINT DEFINITIONS

9.1 PATHOLOGIC RESPONSE – Standard pathologic assessment per our institutional guidelines will be followed. Additionally, we will include calculation of percent cellularity on the biopsy specimen, residual cancer burden (RCB) analysis and repeat evaluation of Ki67 and receptor status (ER, PR and Her2) if there is any residual invasive cancer at surgery. Residual cancer burden will be assessed by staff pathologists and is calculated using a published continuous index that combines pathologic measurements of the primary tumor (size and cellularity) and nodal metastases (number and size) (reference Symanns). This RCB index has been validated as a predictor of distant relapse.

9.2 ACUTE TOXICITY- Acute toxicity will be graded with the Common Terminology Criteria for Adverse Events (CTCAE) version 4. Grade ≥ 3 acute toxicity will be considered severe (Appendix 15.2).

9.3 COSMESIS- As noted in the introduction, early cosmetic results from other published pre-operative radiation series for early stage breast cancer have been favorable.¹¹ We expect similar favorable outcomes, and for the pre-operative single fraction cosmetic results to be equivalent to that of partial breast radiation results. We expect cosmesis to stabilize at 3 years following treatment and thus our endpoint will be to measure results at this timepoint. We will also assess cosmesis at specified time points per the study calendar to quantify changes in breast cosmesis over time.

Cosmetic results will be evaluated by both the patient and the physician. Patients will rate cosmesis using the Breast Cancer Treatment Outcome Scale (BCTOS), which will also be used to evaluate patient reported quality of life (Appendix 15.1). This self-report instrument has been used in a number of studies for this purpose and has both reliability and validity (reference Stanton AL, Krishnan L, Collins CA. Form or function? Part 1. Subjective cosmetic and functional correlates of quality of life in women treated with breast-conserving surgical procedures and radiotherapy. *Cancer* 91:2273-2281, 2001)

October 10, 2023

Principal Investigator: [name]

IRB IRB00128074

Patients will first complete this after informed consent, and then at multiple intervening assessment points up to 3-years of follow-up (see Study Calendar). At the same time points, patients will also score cosmesis using the RTOG 4-point scale.

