13.2 Analysis of secondary objectives

Acute toxicities (up to 90 days after completion of surgery) will be collected using CTCAE v4.0 and will be tabulated by body system, type and grade. The number and percentage of patients who experience at least one grade 3 or higher AE will also be reported. The presence or absence of all CTCAE toxicities included in Appendix 15.2 will be assessed in addition to those listed here: breast pain, dermatitis, atrophy, fatigue, fibrosis, lymphedema, pruritis, seroma, surgical wound dehiscence, fat necrosis, surgical site infection, hyperpigmentation, skin ulceration. We will use continuous toxicity monitoring throughout the trial as described below. Stopping rules are described below in 13.3.

Local recurrence rates will be calculated using cumulative incidence function, where death without local recurrence is considered as competing event. The associated 95% confidence intervals at landmark timepoints including 6 months, 1 year, 2 years and 3 years will also be provided.

Physician assessment of cosmesis (see Section 9.3) will occur at baseline, 4-6 weeks after surgery, 6 months, 1, 2 and 3 years. The secondary endpoint of poor cosmetic outcome is a physician-assessment of unacceptable (fair or poor) cosmesis at any time point through 3 years and/or occurrence of grade 3 or higher toxicity through 3 years. The number and percentage of patients, with 2-sided x% CIs, will be reported. The timepoint of unacceptable cosmesis assessment and of the grade 3 or higher AEs will be summarized descriptively. Additionally, when all enrolled subjects have had 1 year of follow-up, a working group of investigators will be assembled to evaluate cosmesis on all patients.

Patient-reported satisfaction with cosmetic outcome will be assessed at baseline, 6 months, 1, 2 and 3 years. Satisfaction over time will be summarized descriptively and graphically.

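### Section 13.2 counts any grade 3 or higher toxicity as a poor cosmetic outcome, and does not explicitly commit to a 3-year or a patient-rated fair/poor proportion

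*Combined protocol and SAP*

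**What the plan says.** Three sections of the combined protocol and SAP describe the cosmesis endpoint.

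- **Objective 2.2.2** asks for the "rate of poor cosmetic outcomes from both provider and patient perspectives up to 3 years after pre-operative SBRT", using the RTOG scale and digital images. Toxicity is a separate objective (2.2.1), defined as "any CTCAE v4 grade 3 or higher toxicity noted from RT delivery up to 90 days after completion of surgery".
- **Section 9.3** fixes a time: "We expect cosmesis to stabilize at 3 years following treatment and thus our endpoint will be to measure results at this timepoint". It adds: "Cosmetic results will be evaluated by both the patient and the physician". It gives no cut-off.
- **Section 13.2** has the only full definition: a physician rating of "unacceptable (fair or poor) cosmesis at any time point through 3 years and/or occurrence of grade 3 or higher toxicity through 3 years". For this composite, "The number and percentage of patients, with 2-sided x% CIs, will be reported".

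Section 13.2 also plans four related outputs:
- for acute toxicity, "The number and percentage of patients who experience at least one grade 3 or higher AE will also be reported";
- a descriptive summary of when unacceptable ratings and grade 3+ events occur;
- a working-group review of cosmesis once all subjects have 1 year of follow-up;
- a descriptive and graphical summary of patient satisfaction with the cosmetic result.

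The toxicities it names include "breast pain, dermatitis, atrophy, fatigue, fibrosis, lymphedema, pruritis, seroma, surgical wound dehiscence, fat necrosis, surgical site infection". The study calendar (section 8) schedules physician and patient RTOG ratings and toxicity assessment to month 36. Item 3 of the patient form (Appendix 15.3.2) is the same four-category rating that the physician uses.

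**The concern.** The label and the content of the 13.2 endpoint do not match. A single grade 3+ event of any kind is enough for a patient to count as a poor cosmetic outcome, whatever the breast looks like. The definition also differs from 9.3 in time point, and from 2.2.2 in rater and in content.

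Cosmesis is central to the trial's rationale. Section 3.3 cites poorer cosmesis with external-beam partial breast irradiation, and a pilot in which every patient was rated excellent or good. Section 9.3 expects results equivalent to those of partial breast radiation. A percentage that mixes any-time ratings with toxicity cannot be set against cosmesis-only results. In addition, one of the two perspectives named in 2.2.2, the patient's, has no explicitly specified rate.

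**Working it through.** **1. The definitions side by side**

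| | 2.2.2 | 9.3 | 13.2 |
|---|---|---|---|
| Time | up to 3 years | at 3 years | any time point through 3 years |
| Rater | provider and patient | patient and physician | physician |
| Cut-off | poor outcome, undefined | none stated | fair or poor |
| Toxicity | no | no | any grade 3+, sufficient alone |

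The time conflict is between 13.2 and 9.3; the wording of 2.2.2 fits an any-time measure. The conflict over the patient rate is mainly between 13.2 and 2.2.2. The toxicity component appears only in 13.2. Read literally, any time point also includes the baseline rating, because 13.2 lists baseline among the physician assessments.

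**2. What follows from the definition**

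Let A be the patients with acute grade 3+ toxicity (2.2.1), T those with grade 3+ toxicity through 3 years, C those ever rated fair or poor by the physician, and C3 those so rated at 3 years. Section 13.2 reports C ∪ T.

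- The acute window lies inside the 3 years, so A ⊆ T ⊆ C ∪ T. With a common denominator, the reported rate is at least the acute grade 3+ rate.
- With complete ratings, C3 ⊆ C ⊆ C ∪ T. The reported rate is at least the 3-year fair/poor proportion. It is higher whenever an early fair or poor rating resolves, or a grade 3+ event occurs in a patient rated good or excellent.

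**3. Size (illustration only)**

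The documents give no expected cosmesis rate. The inputs are n = 40 (13.1) and, from 13.3, an assumed acute grade 3+ risk of about 5%, a monitoring threshold of 10%, and a Beta(1,20) prior. The prior reproduces its description: mean 1/21 = 4.8%, and P(risk > 10%) = 0.9^20 = 0.122.

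Assume no patient is ever rated fair or poor, and count acute events only:

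- Risk 5%: expected 40 × 0.05 = 2; P(at least one) = 1 − 0.95^40 = 0.871.
- Risk 10%: expected 40 × 0.10 = 4; P(at least one) = 1 − 0.90^40 = 0.985.
- Averaged over the prior: expected 40/21 = 1.9; P(none) = 20/60, so P(at least one) = 0.667.

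Each such patient adds 1/40 = 2.5 percentage points.

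If instead 5% were ever rated fair or poor (an assumption) and toxicity risk were 5%, the composite would be 1 − 0.95 × 0.95 = 9.75% under independence. It would be 5% with full overlap and 10% with none.

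**4. The confidence level**

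Section 13.2 leaves the level as a placeholder. Section 13.1 uses 90% and the local recurrence analysis uses 95%, so neither is an obvious default. For 2 of 40, the exact two-sided interval is 0.9% to 14.9% at 90% and 0.6% to 16.9% at 95%.

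**The case against.** A composite of unacceptable cosmesis or severe toxicity can be a deliberate choice. Most toxicities named in 13.2 are breast, skin or wound events that may well affect appearance; fatigue is the clear exception. The endpoint is descriptive, and acute toxicity and event timing are reported separately. The pilot summary in 3.3 reports no grade 3 or 4 toxicities in 32 patients (though also 3% grade 3 fibrosis at 18 months, itself relevant to cosmesis). On that experience, inflation from non-cosmetic events could be close to zero. All of this stands, and it limits the size of the problem. It does not repair the label, or the difference from 9.3 and 2.2.2.

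The other planned outputs do not close the gap. The timing summary describes patients with events and is not a proportion with a denominator. The working-group review is triggered at 1 year of follow-up, not 3.

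Three stronger readings are tempting but not supported:

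- A reader might infer that 2.2.2 and 9.3 both promise a fair/poor proportion at the 3-year visit. Neither does. Section 9.3 only says that results will be measured then, without a cut-off, and 2.2.2 covers the period up to 3 years.
- A reader might infer that patient fair/poor percentages will not be produced. The satisfaction summary in 13.2 names no instrument and could include them. They are simply not specified.
- A reader might infer that section 10.1 stops adverse event collection 90 days after surgery, so that 3-year toxicity cannot be captured. That section also refers to collection across the whole study, which may cover the assessments to month 36. The text is ambiguous rather than contradictory.

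**Conclusion.** The point holds as a problem of definition and reporting. Followed as written, 13.2 yields a rate labelled poor cosmetic outcome that includes patients with good or excellent cosmesis. That rate cannot be lower than the acute grade 3+ rate, and it is not the 3-year result that 9.3 describes. A 3-year fair/poor proportion and a patient-rated one are not explicitly committed to, although the ratings are collected.

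The size is uncertain. The figures of 2 of 40 and 4 of 40 rest on the protocol's monitoring assumptions for acute toxicity and on no fair or poor ratings. The true inflation could be near zero if severe toxicity is as rare as in the pilot. A reader might infer that the trial's conclusion is at risk; it is not, because no decision rule uses this endpoint. The change should still be made, since it concerns a named secondary objective and uses data already planned.

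**What to change.** Align 2.2.2, 9.3 and 13.2, and in 13.2 report:

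1. the physician RTOG fair/poor proportion at 3 years, with the number of patients rated;
2. physician fair/poor at any post-treatment visit through 3 years, labelled as a cumulative measure (this removes the baseline rating);
3. the patient RTOG fair/poor proportion at 3 years;
4. grade 3+ toxicity through 3 years on its own line, after clarifying whether the collection period in 10.1 covers the calendar's toxicity assessments to month 36.

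If the composite is kept, name it for what it contains: fair/poor cosmesis or grade 3+ toxicity. Replace the placeholder confidence level with a stated one.

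**Cost.** A protocol amendment with IRB approval (12.4). No new visits or data are needed. Patients without a 3-year rating drop out of the 3-year proportions, which is why the number rated should be shown. Taking toxicity out can only lower or leave unchanged the reported cosmesis rate, so the toxicity line should stand beside it.

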6.7.2 ADJUVANT SYSTEMIC THERAPY

Adjuvant systemic therapies including chemotherapy and endocrine therapy will be at the discretion of the medical oncologist. If Oncotype DX or other genetic scoring is desired for evaluation, this will be sent on the pre-treatment biopsy specimen obtained before enrollment on study and which was used for initial diagnosis. Medical oncology approval via case discussion or formal consultation is required prior to pre-operative SBRT to ensure the medical oncologist will be able to obtain all needed information to determine adjuvant systemic recommendations.

6.8 CRITERIA FOR DISCONTINUATION FROM PROTOCOL TREATMENT.

Because SBRT is delivered in one day, discontinuation is unlikely. However if at any time the constraints of this protocol are detrimental to the patient's health and/or the patient no longer wishes to continue on the study long-term, the patient shall be removed from the protocol follow-up. In this event the reason(s) for discontinuation of study participation will be noted by the PI in the Radiation Oncology record. Subjects who prematurely withdraw will not be replaced unless radiation has not been initiated. Reasons for PI-initiated withdrawal may include, but is not limited to the following:

- Adverse events
- Abnormal laboratory values
- Abnormal test procedure results
- Protocol deviation
- Administrative issues
- Disease progression

6.9 DURATION OF THERAPY:

The duration of protocol-specified therapy will be approximately 2 months. It is expected that treatment planning may take 2 weeks from simulation to treatment delivery, and that 4-6 weeks will elapse from treatment delivery to surgery.

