13. STATISTICAL CONSIDERATIONS

This is a prospective, single-arm study to determine the pathologic outcomes, acute toxicities, cosmetic outcomes, and local recurrence rates of preoperative single fraction partial breast radiation in early stage breast cancer. All analyses will be undertaken in the enrolled population who initiate treatment.

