Appendix 15.3.1 RTOG cosmesis scale- PHYSICIAN FORM

1	EXCELLENT: when compared to the untreated breast or the original appearance of the breast, there is minimal or no difference in the size or shape of the treated breast. The way the breast feels (its texture) is the same or slightly different. There may be thickening, scar tissue or fluid accumulation within the breast, but not enough to change the appearance.
2	GOOD: there is a slight difference in the size or shape of the treated breast as compared to the opposite breast or the original appearance of the treated breast. There may be some mild reddening or darkening of the breast. The thickening or scar tissue within the breast causes only a mild change in the shape or size.
3	FAIR: obvious differences in the size and shape of the treated breast. This change involves a quarter or less of the breast. There can be moderate thickening or scar tissue of the skin and the breast, and there may be obvious color changes.
4	POOR: marked change in the appearance of the treated breast involving more than a quarter of the breast tissue. The skin changes may be obvious and detract from the appearance of the breast. Severe scarring and thickening of the breast, which clearly alters the appearance of the breast, may be found.

(Circle the number next to the word that best describes the cosmetic results.)

	None	Yes, present but does not affect cosmesis	Yes, present and affects cosmesis
Skin telangiectasia	0	1	2
Skin atrophy	0	1	2
Pigment change	0	1	2
Erythema	0	1	2
Fat necrosis	0	1	2
Fibrosis	0	1	2
Retraction or contour defect	0	1	2
Breast shrinkage	0	1	2
Other significant tx effects Specify: _____	0	1	2

October 10, 2023

Principal Investigator: [name]

IRB IRB00128074

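### Section 13.2 reports 3-year poor cosmetic outcome as a crude percentage of all treated patients, so those who withdraw before either component occurs count as non-events by default, which lowers the rate

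*Combined protocol and SAP*

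**What the plan says.** All of this is in the combined protocol and SAP.

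- **Endpoint (13.2).** A composite: a physician rating of "unacceptable (fair or poor) cosmesis at any time point through 3 years and/or occurrence of grade 3 or higher toxicity through 3 years".
- **Estimator (13.2).** "The number and percentage of patients, with 2-sided x% CIs, will be reported". The confidence level is still a placeholder.
- **Population (13).** "All analyses will be undertaken in the enrolled population who initiate treatment".
- **Withdrawal (6.8).** In the event of early discontinuation "the patient shall be removed from the protocol follow-up", and "Subjects who prematurely withdraw will not be replaced unless radiation has not been initiated". Adverse events and disease progression are among the listed reasons for investigator-initiated withdrawal.
- **Rating schedule (13.2).** Physician assessment "will occur at baseline, 4-6 weeks after surgery, 6 months, 1, 2 and 3 years". The study calendar (section 8) allows one month either side of the follow-up visits. It also schedules toxicity assessment at months 18 and 30, when cosmesis is not rated.
- **Local recurrence (13.2).** "Local recurrence rates will be calculated using cumulative incidence function, where death without local recurrence is considered as competing event", with intervals at 6 months, 1, 2 and 3 years.

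For poor cosmetic outcome the plan gives no rule for missed ratings, withdrawal, death or mastectomy, and it defines no evaluable set.

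**The concern.** An outcome that can occur at any time over 3 years needs 3 years of observation before its absence is known. A patient rated good at 6 months who then withdraws has been observed for a small part of that period. Read literally, sections 13 and 13.2 still put her in the denominator as a patient without a poor outcome.

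Local recurrence, in the same patients over the same 3 years, gets an estimator that accommodates incomplete follow-up. No reason is given for the difference.

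Cosmesis is a stated secondary objective (2.2.2) and central to the rationale: section 3.3 faults external-beam partial breast irradiation for poorer cosmesis, and section 9.3 expects results equivalent to partial breast radiation. A rate lowered by withdrawal favours that expectation. Section 9.3 also expects cosmesis to stabilise only at 3 years, so early exits miss follow-up that matters.

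**Working it through.** **Plan's own figure.** None is stated for this endpoint, and no withdrawal, death, mastectomy or cosmesis rate is given. Only the maximum of 40 patients (13.1) comes from the documents. Every rate below is an assumption.

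**1. Withdrawal.** Let π be the true 3-year risk of the composite and d the share who would drop out by 3 years, both with constant hazards:

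- h = −ln(1 − π)/3 and c = −ln(1 − d)/3
- crude percentage = h/(h + c) × [1 − (1 − π)(1 − d)]

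A cumulative incidence that censors withdrawals estimates π itself.

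For π = 0.20, h = 0.0744:

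- d = 0.10: c = 0.0351; 0.679 × 0.28 = 19.0%
- d = 0.20: c = h; 0.5 × 0.36 = 18.0%
- d = 0.30: c = 0.1189; 0.385 × 0.44 = 16.9%

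| True 3-year risk | 10% dropout | 20% dropout | 30% dropout |
|---|---|---|---|
| 20% | 19.0% | 18.0% | 16.9% |
| 30% | 28.6% | 27.1% | 25.5% |

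In 40 patients with a true 20%, the shortfall is 40 × 0.010 = 0.4, 40 × 0.020 = 0.8 and 40 × 0.031 = 1.2 patients.

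**2. Death.** Take a 20% risk, 3% deaths per year and no withdrawal. The death hazard is m = −ln(0.97) = 0.0305. Both the crude percentage and the cumulative incidence with death competing equal h/(h + m) × [1 − exp(−3(h + m))] = 0.709 × 0.270 = 19.1%. Death creates no gap between them.

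**3. Mastectomy of the treated breast.** Take a 20% risk, 1% mastectomy and 1% death per year (hazard 0.01005 each) and no withdrawal. The total hazard is 0.0945, and 1 − exp(−3 × 0.0945) = 0.247.

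- Mastectomy as a competing event: 0.0744/0.0945 × 0.247 = 19.4%, the same as the crude percentage.
- Mastectomy as a failure: (0.0744 + 0.01005)/0.0945 × 0.247 = 22.1%.

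The difference comes from the definition, which the plan does not give. The physician form (Appendix 15.3.1) describes the treated breast, for example "marked change in the appearance of the treated breast involving more than a quarter of the breast tissue", so a rule is needed once that breast is gone.

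**4. How much the missing rule leaves open.** For 40 treated patients:

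| Events | Lost without event | Crude | Excluding lost | All lost counted as failures |
|---|---|---|---|---|
| 4 | 4 | 4/40 = 10.0% | 4/36 = 11.1% | 8/40 = 20.0% |
| 8 | 8 | 8/40 = 20.0% | 8/32 = 25.0% | 16/40 = 40.0% |

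**The case against.** The strongest reply has four parts.

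**The plan is silent rather than wrong.** Nowhere does it say that an unrated patient is acceptable. That is right, and a reader should not infer that it does. But a percentage over all treated patients produces that result by default, and excluding unrated patients would depart from section 13.

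**The effect is small.** At a true 20% the shift is about one patient or less, while the exact 95% interval for 8 of 40 is 9.1% to 35.6%. The endpoint is secondary and descriptive, with no test or margin. Section 13.2 already summarises event timing and adds a working-group evaluation of all patients after 1 year. This stands, and it limits the weight of the point. Constant hazards are also an assumption: if events mostly precede dropout, the shift is smaller.

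**The direction is not settled.** A reader might infer that the final figure must be too low. The documents do not support that. Baseline is on the rating schedule and is not excluded, and transient early ratings count, which raises the figure relative to the 3-year status named in section 9.3. A patient with grade 3 or higher toxicity before leaving is already an event. Only the withdrawal effect has a known direction.

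**Death and mastectomy are not clear errors.** A reader might infer that both are miscounted as good results. Death is not, if it competes. Mastectomy lowers the rate only if it is defined as failure, which no section does. Sections 6.5 and 6.7.1 answer inadequate margins with re-excision or whole-breast radiation, and planned mastectomy is an exclusion (4.2.7).

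**Conclusion.** The point holds for withdrawals. Applied literally, the estimator in 13.2 counts patients who leave before either component occurs as non-events and so lowers the reported rate. At a true 20% the loss is about 1 to 3 percentage points for 10% to 30% dropout, given constant hazards and dropout unrelated to outcome. It would be larger if patients with poor results leave more often, which is plausible because adverse events are a listed reason for withdrawal. The documents do not support a claim that the plan deliberately scores unrated patients as acceptable, that deaths bias the rate, that mastectomy necessarily does, or that the net figure is too low. This is a modest but real weakness in a secondary endpoint and should be corrected before analysis.

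**What to change.** In 13.2, replace the crude percentage with the cumulative incidence of first poor cosmetic outcome (either component) at 6 months, 1, 2 and 3 years, the landmarks already used for local recurrence, and specify:

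- Count post-treatment ratings only, and assign events to the nominal visit, so that a month-36 rating made within its window is included.
- Treat death as a competing event.
- Censor withdrawals at the last completed assessment of the composite. Censoring at the last cosmesis rating would discard toxicity follow-up from months 18 and 30.
- Pre-specify mastectomy of the treated breast, for example as a competing event with a sensitivity analysis counting it as failure, and list those patients.
- Report the number rated at each visit, and a best/worst-case bound for patients lost without an event, because censoring does not remove bias if withdrawal is informative.
- Fill in the confidence level.

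The cost is SAP wording and a little more analysis, using data already scheduled. The estimate will be slightly higher where patients withdraw, and its interval slightly wider.
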